**(1) Physician-diagnosed asthma (based on EHR).**

**(2) Persistent or uncontrolled asthma as per clinic assessment.** Based on NHLBI guidelines, any one of the following: in past month, > 2 days/week with asthma symptoms, >2 days/week with rescue medication use, >2 days/month with nighttime symptoms, or ≥ 2 episodes in the past year that required systemic corticosteroids.

1) Mild persistent or more severe asthma severity, or poor asthma control (see definitions below). \*A different assessment of eligibility will be performed depending on whether or not the child has a current prescription for preventive asthma medication at baseline and parent reports its use. This is consistent with the EPR recommendations that make a strong distinction between classifying asthma severity (for children not using preventive medications) and assessing control (for children using preventive medications). If a child has used a preventive medication in the past, but reports no use of the medication in the prior 3 months, we will assess severity. This 3-month time frame is consistent with the length of "wash-out" time for inhaled steroids.

a) **Children not using a preventive medication at baseline:** Mild persistent to severe persistent asthma. Any 1 of the following, during the prior 4 weeks (as defined by parent interview in the waiting room and EMR review):

- i) An average of >2 days per week with asthma symptoms
- ii) >2 days per week with rescue medication use
- iii) ≥3 nights per month awakened with nighttime symptoms
- iv) Minor limitation of activity
- v) >2 episodes of asthma during the past year that have required systemic corticosteroids

b) **Children using a preventive medication at baseline:** Poor asthma control. Any 1 of the following, during the prior 4 weeks (as defined by parent interview in the waiting room):

- i) An average of >2 days per week with asthma symptoms
- ii) >2 days per week with rescue medication use
- iii) ≥2 nights per month awakened with nighttime symptoms
- iv) Some limitation of activity
- v) >2 episodes of asthma during the past year that have required systemic corticosteroids.

**(3)** Age 2 and 12 years, inclusive.

Additional inclusion criteria will apply to a subset of 512 of children whose caregivers will be interviewed to systematically evaluate experiences with the program and caregiver-reported morbidity outcomes:

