***Exclusion Criteria:***

- (1) The child has other significant medical conditions, such as congenital heart disease, cystic fibrosis, or other chronic lung disease, that could interfere with the assessment of asthma-related measures.

Additional exclusion criteria will apply to a subset of 512 children/caregivers as described above:

- (1) No access to a telephone to conduct follow-up surveys.
- (2) Children in foster care or other situations in which consent cannot be obtained from a guardian.

*Based on our previous studies, we anticipate <10% of children will be excluded based on these criteria.*

**Screening:** In 22 practices, clinic staff (RN/LPN) will ask caregivers of all children 2-12 years of age with asthma to complete a screening survey in EPIC Electronic Health Record (EHR) during the triage portion of their doctor visit. The screening survey questions follow national guidelines and will identify children with persistent or uncontrolled asthma (Appendix A).

**Procedures for enrollment of a subset (n=512):** Clinic staff will inform research team on days of recruitment to obtain consent and baseline assessment from a subset of children with persistent or uncontrolled asthma and their caregivers from whom additional morbidity measures (not present in the EHR) will be collected.

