schedule of OW calls will apply. OWs will use evidence-based educational materials that were previously adapted to the needs of our community, and focus on helping parents develop 6 key asthma management behaviors as per NHLBI guidelines and our prior research using OWs: (1) Asthma control monitoring, (2) Identifying and minimizing exposure to triggers, (3) Effectively using controller medications, (4) Using quick-relief medications, (5) Using an asthma action plan, and (6) Effectively working with the child's physician and schools on optimizing asthma care. The decision to work on specific behaviors will be tailored to caregiver needs expressed at the provider visit and based on caregiver's concerns and goals identified by the caregiver prompt. During the telephone calls, OWs will also assist with patient care activities (e.g., scheduling appointments, refer to community services for Integrated Pest Management provided by the NYC Department of Health, smoking cessation programs (NYS Smokers' Quitline), free legal services and existing on-line resources) and share information with the provider and other members of the clinical team via EHR if any concerns about patient or caregiver arise during the telephone encounters (e.g., caregiver does not have prescription for medication, child seen in ED or hospitalized). The OWs will use a Microsoft Access database to record call frequency, length, and notes taken. These calls will last ~30 minutes. OWs will also send text messages, if preferred by the caregivers, to remind about clinic appointments or schedule follow-up telephone calls.

**Translational Process within eMPI Clinics:** At each intervention clinic, there will be three phases of eMPI translation into routine practice: 1) *initiation* (3 months, intense support provided), 2) *consolidation* (3 months,

Initiation	Consolidation	Sustainability
		support available), and 3) sustainability (18 months, support as needed). During the initiation phase, the goal will be to introduce eMPI to the practice. First, we will partner with a clinic champion , a practice physician who

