will also serve on our *Practice Advisory Board*. The Board will consist of ≥ 2 physicians, 1-2 nurses, 1-2 front desk and administrative staff. The Board will meet monthly during the initiation and consolidation phases to review the study protocol as it relates to the practices, discuss any provider-reported barriers to implementation and identify solutions to address these barriers using a collaborative problem solving approach. These Boards will capitalize on already existing and engaged groups created by the Bronx Ongoing Pediatric Screening in the Medical Home (BOPS) program described in the Preliminary Studies section. To initiate the planning process, we will ask Board members to complete the RE-AIM planning tool to highlight any concerns or barriers to implementation. We will engage providers in a practice improvement process by having the clinic champion discuss feedback received from individual providers and solutions at the regular clinic meetings. We will provide the champion with a tool, updated monthly, to record identified barriers to guideline implementation and ways to address them. We will also collect baseline information on provider corrective actions in EHR; assess provider self-efficacy, provider-caregiver communication, and provider competencies in guideline-based care using a validated survey (Appendix A). During month 1 of the initiation phase, we will provide *practice-level support* (e.g., pocket cards with guidelines, brief interactive seminars, local asthma resources; Appendix C) to the practices to assist providers in implementing the asthma management outlined in the NHLBI guidelines and to help remove practice and provider-level barriers to guideline implementation. The interactive seminars, developed using principles of physician behavior change and led by the PI ([name]) and co-Is ([name], pulmonologist and [name], allergist), will generate enthusiasm around prompting and empower providers to implement desired changes. The seminars will include an overview of guideline-based asthma care and orientation to the prompts, resource guides and the feedback charts. At the end of the seminar, a brief needs assessment survey will be done, and additional resources will be provided based on the needs of the individual practices. Providers will receive continuing education credit for their participation. These sessions will be coordinated by each practice's champion. We will also provide *practice-level feedback*. eMPI practices will receive monthly feedback during the initiation phase on the proportion of visits with appropriate guideline-based preventive actions, and the proportion of patients meeting goals of therapy (limited symptoms, no ED visits/hospitalizations). The feedback will be delivered to the champion who will then share it with the rest of the providers. The information will be presented graphically with other intervention practices displayed by a code for comparison. A Quality Control Tool will be used to measure and assess nurse adoption of the asthma severity/control screening. Research staff will observe nursing staff at least once during the

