
implementation period as they conduct the severity/control asthma screening, make note of their screening practices and provide feedback to the nursing staff and the clinic champion. During the consolidation phase, we will continue to work with site champions and practices to ensure eMPI is implemented as intended and provide support on addressing barriers or concerns. Major activities during this time will include on-going monitoring of all aspects of eMPI, feedback to sites about their performance, identification of barriers and needed resources, and Board meetings to address these impediments. Given the COVID-19 pandemic, as of March 2020, Board meetings have been restricted to telephonic or video conference call only. We will finalize a sustainability plan with each practice to ensure on-going use of guidelines. During sustainability phase, we will observe practices' continued use of guideline-based care. During this time, we will not provide regular consultations or support, but will be available to address questions and concerns that arise. This will allow us to monitor how much outside help sites require to sustain eMPI. We will provide feedback at the practices' request. We expect that eMPI practices undergoing our translational program will increase guideline-based care during a 3-month initiation period and subsequent 3-month consolidation period, and will maintain these gains over an 18-month sustainability period.

**Enhanced Usual Care (eUC) Practices** will receive a review packet of the NAEPP guidelines and educational resources for families. Children will be assessed for asthma severity and level of control at each visit as best-practice care, but active intervention components will not be provided.

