#### **Clinic-Level Variables**

The **primary outcome** is a clinic-level variable measured by the proportion of visits with  $\geq 1$  guideline-based corrective actions. To calculate this proportion, the denominator will include only the visits by patients aged 2-12 years with persistent or uncontrolled asthma at the time of visit. We will obtain these data from the EHR at baseline, monthly during the initiation phase (to provide feedback to eMPI practices) and every 3 months thereafter for 24 months. Corrective actions include: (1) prescription of a new preventive asthma medication; (2) increase in dose of a preventive medication (for children already on preventive medication); (3) evaluation and counseling regarding triggers; (4) treatment of co-morbid conditions (e.g., sinusitis, allergic rhinitis, obesity); (5) referral to an allergy or pulmonary specialist. We will consider children receiving any of these guideline-based preventive care measures during the visit as having a corrective action (as not all actions may be necessary for each patient), and also will consider each component of preventive care separately. We collected prospective data on most items included in the corrective action definition in our prior work. Additional corrective actions include recommendations for a follow-up visit specifically to discuss asthma, referrals made to OW, and provision of an asthma action plan or school medication administration form.

**Covariate:** Practice characteristics will include practice size (small, medium, large), practice type (hospital-based practice, Federally Qualified Health Center, neighborhood health center), and patient mix (pediatrics, adult/pediatrics), involvement of support staff in the delivery of preventive asthma care, practice-level changes (e.g., new asthma-related initiatives in the practice). We will obtain this information from the existing database of practices and from interviews with the physician champion and office administrator at each practice.

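### Quality control of the severity/control screen, which sets the primary denominator in both arms, is described only for eMPI clinics, and no planned analysis would show uneven capture of eligible visits

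*Combined protocol and SAP*

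**What the plan says.** The screen is meant to be common to both arms. The Screening paragraph says "In 22 practices, clinic staff (RN/LPN) will ask caregivers of all children 2-12 years of age with asthma to complete a screening survey". The paragraph on Enhanced Usual Care practices says "Children will be assessed for asthma severity and level of control at each visit as best-practice care, but active intervention components will not be provided".

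The screen also defines the population for the primary outcome. The inclusion criteria require "Persistent or uncontrolled asthma as per clinic assessment", and under Clinic-Level Variables "the denominator will include only the visits by patients aged 2-12 years with persistent or uncontrolled asthma at the time of visit". The Aim 1 analysis uses the same denominator.

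Quality control of the screen appears in one place, the text on the Translational Process within eMPI Clinics. That text opens with "At each intervention clinic, there will be three phases of eMPI translation into routine practice". Within its account of the initiation phase it says "A Quality Control Tool will be used to measure and assess nurse adoption of the asthma severity/control screening". The next sentence begins "Research staff will observe nursing staff at least once during the" implementation period, and adds that these staff will "make note of their screening practices and provide feedback to the nursing staff and the clinic champion".

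The Aim 3 analysis lists caregivers' completion of the assessment among its measures of eMPI implementation. It does not mention a comparison of completion between arms.

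**The concern.** The denominator is formed after randomization, by clinic staff, visit by visit. If the instrument that forms it is observed and improved in one arm and left alone in the other, the two arms' proportions may be taken over differently selected sets of visits.

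The likelier route is completeness. The tool is described as measuring nurse adoption of the screen, so eMPI nurses may simply screen more visits. Accuracy is a second and weaker route, since how the questions are put to caregivers may affect the answers.

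The direction is open. If the visits missed in eUC are mainly marginal cases on which providers act less often, the eUC proportion is raised and the effect understated. If providers would have acted more often at the missed visits, the effect is overstated.

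The matched-pair permutation test gives no protection. Its sign-flip argument needs each clinic's measured proportion to be the same under either assignment when the intervention does not change provider behaviour. Measurement that depends on the arm breaks this, and more visits do not repair it. The planned adjustment in Aim 1 deals with imbalance in clinic characteristics, not with how visits are classified.

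**Working it through.** **1. The plan's own power figure.** Inputs from the Aim 1 Power Analysis: difference 0.25, SD of paired differences 0.20, 11 pairs, two-sided 0.05. Non-centrality = (0.25/0.20) × √11 = 4.15. The noncentral t with 10 df gives power of 96.1%, which agrees with the stated figure of more than 95%.

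Subjects and Setting now gives 18 participating practices, which is 9 pairs if all are paired. Non-centrality is then 1.25 × √9 = 3.75, and power with 8 df is 90.6%. The loss from 96.1% to 90.6% comes from the number of pairs, not from the screen. The 9-pair figure is the baseline below.

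**2. Bias from incomplete capture.** Let s be the share of truly eligible visits that the screen captures. Let g be the corrective-action rate in captured visits minus the rate in missed visits. In each arm

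- true proportion = s × p_captured + (1 − s) × p_missed
- observed proportion = p_captured
- observed − true = (1 − s) × g

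With the same g in both arms, the shift in the eMPI − eUC difference is (s_eUC − s_eMPI) × g. It is zero if capture is equal or if g is zero.

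The documents give neither s nor g, so both are assumed. With s_eMPI = 0.90:

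| s_eUC | Shift for g of 10 / 20 / 30 points | Power at 9 pairs if the shift dilutes a true 25 points | Rejection rate at 9 pairs with no true effect |
|---|---|---|---|
| 0.90 | 0 / 0 / 0 | 90.6% | 5% |
| 0.85 | 0.5 / 1.0 / 1.5 | 89.4 / 88.2 / 86.9% | 5.1 / 5.2 / 5.5% |
| 0.80 | 1 / 2 / 3 | 88.2 / 85.5 / 82.3% | 5.2 / 5.8 / 6.8% |
| 0.70 | 2 / 4 / 6 | 85.5 / 78.7 / 70.5% | 5.8 / 8.3 / 12.5% |
| 0.60 | 3 / 6 / 9 | 82.3 / 70.5 / 55.9% | 6.8 / 12.5 / 22.2% |

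Example: (0.60 − 0.90) × 0.20 = −0.06, so a true 25 points is observed as 19. Shifts are shown as absolute values. If g is negative, the shift has the same size but favours eMPI. The SD of 0.20 is kept throughout.

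**3. A second model.** Suppose half of eligible visits are plainly symptomatic and half marginal. Assume action rates of 80% and 50% in eMPI and 55% and 25% in eUC, a true difference of 25 points. Sensitivity is 95% for plain cases in both arms and 90% for marginal cases in eMPI.

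- eMPI observed = (0.5 × 0.95 × 0.80 + 0.5 × 0.90 × 0.50) / (0.5 × 0.95 + 0.5 × 0.90) = 0.654.
- With eUC marginal sensitivity of 85%, 80%, 70% or 60%, eUC observed is 0.408, 0.413, 0.423 or 0.434.
- The observed difference is 24.6, 24.1, 23.1 or 22.0 points.
- Power at 9 pairs is 89.6%, 88.5%, 85.8% or 82.4%.

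**4. False positives.** Let f be the share of a denominator that is not truly eligible, and let h be the amount by which the action rate is lower in those visits. The shift is (f_eUC − f_eMPI) × h. With f = 10% in eMPI, 20% to 30% in eUC and h of 10 to 30 points, the shift runs from 0.10 × 0.10 = 1 point to 0.20 × 0.30 = 6 points, in favour of eMPI.

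Sections 2 to 4 are illustrations. They show that the sign is not fixed and that the size depends on quantities that the plan neither gives nor proposes to compare between arms.

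**The case against.** The plan never says that quality control is withheld from eUC; that reading rests on where the text stands and on silence. Placement is imperfect evidence here. The same eMPI text contains a provider survey that Provider-Level Variables gives to providers in all practices. Clinic-Level Variables mentions a physician champion at each practice. The RE-AIM text gives advisory board members as an example of stakeholders from both arms. This stands. It makes eMPI-only quality control the natural reading, not a stated fact, and a single sentence in the plan could settle it.

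A reader might infer that eligible visits are in fact identified with different accuracy by arm. The documents do not support that. The tool measures adoption, caregivers answer the survey, eligibility rests mostly on numeric thresholds, and the contrast may amount to one observation with feedback. Little nurse judgement is described. This also stands, and it is why uneven completion is the more plausible route and why large gaps in capture are hard to justify from the text.

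It can also be said that screen completion is already measured. It is, but as a measure of eMPI implementation, with no stated comparison with eUC. Nor is there a rule for unscreened visits or an alternative denominator.

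**Conclusion.** The concern holds as a risk of differential ascertainment in the primary outcome. The screen is common to both arms and sets the denominator, its quality control is described only for eMPI clinics, and nothing planned would detect uneven capture. That unequal capture occurs is not shown, and neither its direction nor its size can be derived from the documents.

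Under the assumed inputs, a gap of 5 to 10 percentage points in capture moves the primary difference by 0.5 to 3 points, which is small against 25. A gap of 20 to 30 points moves it by 2 to 9 points and would matter, but nothing in the documents supports a gap that large. The correction is worth making because it is cheap and protects the primary result.

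**What to change.** 1. State that the Quality Control Tool is used in all participating practices, with the same number of nurse observations, the same checklist, and feedback limited to how the screen is given. Keep prompts, performance feedback and champion activities in eMPI only. If this is already the practice, say so.
2. In addition, and in any case where practices have finished, report from the EHR, by arm and period, the screen completion rate, the positivity rate and the distribution of the screening items. This is needed even with equal checks, because the screen feeds prompts only in eMPI and staff may have different reasons to complete it. State how unscreened visits are handled.
3. Add a sensitivity analysis of the primary comparison with the same matched-pair permutation test, using all visits by children aged 2-12 with EHR-diagnosed asthma as the denominator.
4. Treat standardisation to a common screening-severity mix as supportive only. It cannot recover unscreened visits, and it adjusts on the items whose recording is in question.

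Cost: with 18 practices and one observation each, about nine extra sessions in eUC. Research staff already attend each clinic 2-3 days a week until monthly enrolment goals are met. eUC screening would become slightly better than it would be unaided, but screening is already part of eUC.

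The all-asthma denominator dilutes the effect. Subjects and Setting estimates that about 50% of children with asthma have persistent or uncontrolled disease. If visits split the same way and other visits show no effect, 25 points becomes about 0.5 × 25 = 12.5. That analysis is a check on direction and consistency, not a replacement for the primary result.

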#### **Clinic-Level Variables**

The **primary outcome** is a clinic-level variable measured by the proportion of visits with  $\geq 1$  guideline-based corrective actions. To calculate this proportion, the denominator will include only the visits by patients aged 2-12 years with persistent or uncontrolled asthma at the time of visit. We will obtain these data from the EHR at baseline, monthly during the initiation phase (to provide feedback to eMPI practices) and every 3 months thereafter for 24 months. Corrective actions include: (1) prescription of a new preventive asthma medication; (2) increase in dose of a preventive medication (for children already on preventive medication); (3) evaluation and counseling regarding triggers; (4) treatment of co-morbid conditions (e.g., sinusitis, allergic rhinitis, obesity); (5) referral to an allergy or pulmonary specialist. We will consider children receiving any of these guideline-based preventive care measures during the visit as having a corrective action (as not all actions may be necessary for each patient), and also will consider each component of preventive care separately. We collected prospective data on most items included in the corrective action definition in our prior work. Additional corrective actions include recommendations for a follow-up visit specifically to discuss asthma, referrals made to OW, and provision of an asthma action plan or school medication administration form.

**Covariate:** Practice characteristics will include practice size (small, medium, large), practice type (hospital-based practice, Federally Qualified Health Center, neighborhood health center), and patient mix (pediatrics, adult/pediatrics), involvement of support staff in the delivery of preventive asthma care, practice-level changes (e.g., new asthma-related initiatives in the practice). We will obtain this information from the existing database of practices and from interviews with the physician champion and office administrator at each practice.

